9.3 Populations for Analyses

- Safety Analysis Dataset: This will include participants who took at least one dose of burosomab.
- Efficacy Analysis Dataset: This will include all participants who received at least one dose of burosomab and have sufficient post-baseline assessment data to enable analyses of study endpoints. For the proportions evaluated at week 48 (the primary endpoint and some secondary endpoints), subjects who have completed 48 weeks of therapy and returned for the week 48 assessment will be included in the analysis.

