Following this initial dose titration phase, doses may be titrated at later weeks at the discretion of the PI, if there are concerns about safety, suboptimal efficacy, or if a subject has not yet achieved the target range of serum phosphate. To optimize serum phosphate levels throughout the dose cycle, Investigators may increase the dose of burosumab in 0.5 mg/kg increments in those subjects whose trough serum phosphate level (just prior to the next dose) is below the lower limit of the target range on 2 consecutive measurements performed at 4-week intervals (**Table 6**).

Table 6. Burosumab Dose Titration Scheme

Study Week	Serum Phosphate Level Z-score ¹	Dose Adjustment
Week 2	Less than -1	Increase the dose by 0.2 to 0.5 mg/kg at next dose
Week 2 6, 10 (adults)	> +2 ³	Decrease the dose by 0.2 to 0.5 mg/kg
Week 1, 2, 3 (pediatrics)		
Weeks 4, 8, 12, 16, 20, 24, 28, 32, 36, 40, 44	Less than -1 ²	Increase the dose by 0.2 to 0.5 mg/kg
	-1 to +2	Continue the current dose
	> +2 ³	Skip dose

¹ See **Table 5** for target phosphate levels according to age and sex-adjusted Z-scores

² If phosphate levels are below –1 standard deviation on 2 consecutive measurements, the burosumab dose may be increased by 0.5 mg/kg

³ If phosphate is Z-score > +2, withhold the next dose and reassess the serum phosphate level in 2 weeks. Once serum phosphate is in target range or less than Z-score –1, treatment may be restarted at 0.2 mg/kg less than prior administered dose. If more than 2 sequential phosphate measurements are > +2 Z-score range, the patient may be considered for study discontinuation.

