6.1.2.1 Dose Limiting Toxicity

A dose limiting toxicity is defined as the occurrence of any of the following:

- A Grade ≥ 3 toxicity that is probably or possibly related to the investigational product, defined according to the Common Terminology Criteria for Adverse Events (CTCAE) Version 5.0.
- A confirmed serum phosphate level of ≥ 8 mg/dL for pediatric subjects, or ≥ 6.5 mg/dL for adult subjects (defined as hyperphosphatemia) at any time after dosing.

If a subject experiences a dose limiting toxicity, the planned dosing for that subject will be evaluated by the Investigators. The outcome of this investigation will determine the subject's continuation or withdrawal from the study, as described in the Section Discontinuation of Study Intervention.

The following laboratory abnormalities will necessitate discontinuation of study drug:

- Documented decline in estimated glomerular filtration rate (eGFR) to <30 mL/min/1.73m² for pediatric patients, or <30 mL/min for adults

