6.5 Concomitant Therapy

At screening and enrollment, the study staff at NIH will question each subject specifically on the use of all concomitant medications and record the medication, dosage, and duration of use in the appropriate CRF. In general, upon admission and throughout the study, site staff will monitor, record, and administer all concomitant medications during the NIH stay. Investigators may

prescribe any concomitant medications or treatments deemed necessary to provide adequate supportive care.

All subjects who are receiving conventional therapy at screening will be instructed to stop taking pharmacologic vitamin D metabolites or analogs (e.g., calcitriol, alfacalcidiol, doxercalciferol, and paricalcitol) and oral phosphate supplements on Week -2. These medications will remain prohibited throughout the conduct of the study. Any subject who resumes or requires the use of any of these medications will be discontinued from the study. Patient safety during this washout time period will be monitored and adverse events will be reported as described in Section [10.5](#).

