7 STUDY INTERVENTION DISCONTINUATION AND PARTICIPANT DISCONTINUATION/WITHDRAWAL

7.1 Study Intervention Discontinuation

Discontinuation from burosomab does not mean discontinuation from the study, and remaining study procedures should be completed as indicated by the study protocol. If a clinically significant finding is identified after enrollment (including, but not limited to changes from baseline), the investigator or qualified designee will determine if any change in participant management is needed. Any new clinically relevant finding will be reported as an adverse event (AE).

The data to be collected at the time of study intervention discontinuation for subjects who prematurely discontinue burosomab will include the following, as described in detail in Section [10.8](#):

- NIH lab tests
- Physical Medicine and Rehabilitation evaluation
- Administration of questionnaires for patient-reported outcomes
- Activities of Daily Living questionnaires

Subjects are free to withdraw from participation in the study at any time upon request.

An investigator may discontinue or withdraw a subject from the study for the following reasons:

- Completion of study intervention
- If any clinical adverse event (AE), laboratory abnormality, or other medical condition or situation occurs such that continued participation in the study would not be in the best interest of the participant
- Investigator discretion
- Positive pregnancy test
- Subject unable to receive burosomab for 12 weeks

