9 STATISTICAL CONSIDERATIONS

9.1 Statistical Hypothesis

This single-arm open-label trial is to gather preliminary information on the effectiveness and safety of burosumab in FD patients. Estimates for the primary and secondary endpoints will be provided.

- Primary Endpoint: The proportion of subjects achieving serum phosphate levels within the target range (Z-score -1 to +2) at Week 48.
- Secondary Endpoints:
 - Proportion of subjects achieving serum phosphate levels within the target range (Z-score -1 to +2) at Week 24
 - Adverse events and clinical safety laboratory tests for up to 4 weeks following the final burosumab dose (48 weeks for adults, 50 weeks for children).
 - Proportion of subjects achieving mean serum phosphate levels above the target range (Z-score >+2), as averaged across dose cycles between Baseline and Week 48
 - Change and percent change from baseline to post-baseline visits in serum phosphate, serum 1,25(OH)2D, ratio of renal tubular maximum reabsorption rate of phosphate to glomerular filtration rate (TmP/GFR)
 - Change in FD lesion activity using ¹⁸F-NaF PET/CT total lesion activity from baseline to 48 weeks

- Change and percent change in serum bone turnover markers, including procollagen 1 N-terminal propeptide (P1NP), beta crosslaps C-telopeptides (CTX), osteocalcin, and bone-specific alkaline phosphatase from baseline to 48 weeks
- Change in FD lesion histology and cell proliferation as assessed by minimally invasive bone biopsies from baseline to 48 weeks (adults with capacity to consent only) from baseline to 48 weeks
- Change from baseline to 48 weeks in muscle strength, range-of-motion, and walking speed (9-minute walk)
- Change from baseline to 48 weeks in patient reported outcomes measures: SF36 (adults), SF10 (children), Brief Pain Inventory (adults and children), Brief Fatigue Inventory (adults and children)

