9.4.2 Analysis of the Primary Endpoints

The 95% Clopper-Pearson exact confidence interval will be calculated for the proportion of subjects achieving serum phosphate levels within the target range (Z-score -1 to +2) at Week 48. The primary endpoint will be evaluated in the Efficacy Analysis Dataset.

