9.4.3 Analysis of the Secondary Endpoint(s)

The 95% Clopper-Pearson exact confidence interval will be provided for the proportions listed in the secondary endpoints. P-values will be calculated. This will be done in the Efficacy Analysis Dataset. If data is missing for categorical outcomes, it will be imputed by either carrying the last observation forward or assuming non-response.

For change from baseline type of secondary endpoints, baseline scores and change over time scores will be summarized by mean, standard deviation, median, and interquartile range. Linear mixed models will be used to analyze the longitudinal change scores collected at multiple post baseline visits if normality assumption is met. The confidence interval will be calculated for change scores at Week 48 based on these models. P-values will be provided as well. All subjects with any data at post baseline visits will be included in these models. For outcomes variables that are collected only at Week 48 post baseline, a 95% confidence interval and the *p* value from the one-sample *t* test will be reported for the change score (from baseline to Week 48)

If the normality assumption is violated when fitting the linear mixed effects models to the raw data, other common transformation methods (such as log or square-root transformation will be explored. If no suitable transformation method is found, *p*-values will be reported by using the exact Wilcoxon signed rank test.

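### The only planned Week 48 primary estimate covers subjects who completed therapy and returned; without an all-dosed figure beside it, phosphate-linked exits can bias it upward by an unknown, possibly zero, amount

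*Combined protocol and SAP*

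**What the plan says.** Section 9.3 first defines the Efficacy Analysis Dataset broadly: at least one dose and enough post-baseline data. For proportions evaluated at Week 48, with the primary endpoint named, it then narrows the set: "subjects who have completed 48 weeks of therapy and returned for the week 48 assessment will be included in the analysis". Section 9.4.2 specifies the 95% Clopper-Pearson interval and says "The primary endpoint will be evaluated in the Efficacy Analysis Dataset". It gives no sensitivity analysis.

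The missing-data text elsewhere does not reach this endpoint. Section 9.4.1 covers longitudinal continuous data only. Section 9.4.3, on secondary endpoints, says "If data is missing for categorical outcomes, it will be imputed by either carrying the last observation forward or assuming non-response".

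Three exit routes can be tied to phosphate:

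- Section 6.5, on oral phosphate and active vitamin D: "Any subject who resumes or requires the use of any of these medications will be discontinued from the study". This is mandatory.
- Section 6.1.2, Table 6 footnote 3: "If more than 2 sequential phosphate measurements are > +2 Z-score range, the patient may be considered for study discontinuation". This is discretionary.
- Section 6.1.2.1, which counts confirmed hyperphosphatemia as a dose limiting toxicity: "The outcome of this investigation will determine the subject's continuation or withdrawal from the study". This is also discretionary.

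For subjects who stop the drug, section 7.1 says "Discontinuation from burosomab does not mean discontinuation from the study, and remaining study procedures should be completed".

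**The concern.** The endpoint is phosphate in range, and some ways of leaving the primary analysis depend on phosphate. A subject who leaves by such a route drops out of both numerator and denominator, so a treatment failure can vanish instead of counting against the drug. A subject who stops burosumab and still returns at Week 48 has an observed value that the primary analysis does not use.

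The trial has no control arm, and the primary result is one proportion with its interval. With about ten subjects, one or two people move it materially. As planned, it estimates success among completers, and no planned Week 48 proportion shows how far that depends on who left.

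The concern has limits. Low phosphate by itself leads to titration, and a completer who is low at Week 48 counts as a failure. Resuming phosphate or vitamin D need not mean that burosumab failed. Exits unrelated to phosphate need not bias the completer figure.

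**Working it through.** **Inputs.** Section 9.2: 10 subjects with 48 weeks of follow-up, 15 recruited to secure them, expected proportion 0.9, two-sided 95% Clopper-Pearson interval. Section 4.1: 15 is a maximum. Section 2.3.1: hyperphosphatemia in 6% of treated adults with XLH and 7% with TIO, managed by dose reduction; none reported in the pediatric studies; every patient in pediatric Study 1 completed 64 weeks.

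**Formula.** For x in range out of n, the lower limit is the 0.025 quantile of Beta(x, n−x+1) and the upper limit is the 0.975 quantile of Beta(x+1, n−x).

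**The plan's own figures.** With n = 10 and x = 10p, the widths for p = 0.5, 0.6, 0.7, 0.8, 0.9 and 0.95 are 0.626, 0.616, 0.586, 0.531, 0.442 and 0.381. Table 7 gives 0.63, 0.62, 0.59, 0.53, 0.44 and 0.38, so it reproduces.

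**Illustration (assumed, not forecast).** 15 are dosed, 10 complete, and 9 of the 10 are in range. Of the 5 leavers, k failed on phosphate, and the others are set aside. The reference proportion is 9/(10+k). The completer error is 9/10 minus that, and the all-dosed error is 9/15 minus that.

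| k | 9/(10+k) | 95% CI | Completer error (points) | All-dosed error (points) |
|---|---|---|---|---|
| 0 | 90.0% | 0.555–0.997 | 0 | −30.0 |
| 1 | 81.8% | 0.482–0.977 | +8.2 | −21.8 |
| 2 | 75.0% | 0.428–0.945 | +15.0 | −15.0 |
| 3 | 69.2% | 0.386–0.909 | +20.8 | −9.2 |
| 4 | 64.3% | 0.351–0.872 | +25.7 | −4.3 |
| 5 | 60.0% | 0.323–0.837 | +30.0 | 0 |

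With 12 completers, 11 in range (91.7%) and 3 leavers, the completer overstatement is 0 at k = 0, 7.1 points at k = 1 (11/13 = 84.6%) and 13.1 points at k = 2 (11/14 = 78.6%).

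The direction is not guaranteed. If all five leavers were in fact in range, the all-dosed proportion would be 14/15 = 93.3% (0.681–0.998), and the completer figure would be 3.3 points too low.

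**Which k is plausible?** For the high-phosphate routes, 15 × 0.06 = 0.90 and 15 × 0.07 = 1.05 events, if adult rates are applied to all 15. These are events, not exits, and section 2.3.1 describes them as managed by dose reduction. That points to k near zero for those routes, with the caveat that the evidence comes from other diseases. For the section 6.5 route the documents give no rate.

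**The case against.** The strongest reply is that the plan is open about what it does. Section 9.3 states an exclusion rule, section 9.2 sizes the trial on 10 subjects with 48 weeks of follow-up, and section 9.1 claims only preliminary estimates, with no threshold to pass. A reader might infer that the plan has no rule for non-completers. That is not so: the rule is exclusion, and what is missing is a companion figure.

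Dropouts are not invisible either. The mixed models in section 9.4.3 keep everyone with post-baseline data, section 9.4.4 tabulates adverse events leading to discontinuation in all dosed subjects, and the secondary endpoint "Proportion of subjects achieving serum phosphate levels within the target range (Z-score -1 to +2) at Week 24" can reflect exits before Week 24. This stands, but none of it gives the Week 48 in-range proportion among treated subjects, and the Week 24 figure cannot reflect later exits. A reader could divide the number in range by the number dosed, but would have no stated treatment of subjects who stopped the drug and returned.

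A reader might also infer that the all-dosed proportion should become the primary analysis. The documents do not support that. In the illustration it is further from the reference than the completer figure at k = 0 and 1, ties at k = 2, and is closer only from k = 3. It would also depart from the precision basis in section 9.2: the interval for 9/15 is 0.514 wide, against the stated 0.44.

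Reading the section 9.4.3 imputation sentence across to the primary would not settle the matter. It leaves two options open, and section 9.3 has already removed the subjects it would impute.

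**Conclusion.** The gap in the wording is certain; the bias is only possible. The sole planned primary estimate is conditional on completing therapy and returning, and phosphate-linked exits can push it upward. With 9 of 10 completers in range, the overstatement is 8.2 points for one phosphate-failure exit and 15.0 for two. A reader might take the 30 points at k = 5 as the expected bias. It is a ceiling that needs all five spare places to be dosed subjects who left as phosphate failures, and nothing in the documents suggests that. They report no exits from hyperphosphatemia in XLH or TIO, give no exit rate for FD and none for the section 6.5 route, so the true figure may be zero. This is a cheap improvement to reporting, not a flaw that invalidates the primary analysis.

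**What to change.** Keep the completer proportion in section 9.3 and the N = 10 precision statement in section 9.2. Add to section 9.4.2 that the Week 48 proportion, with its Clopper-Pearson interval, is always reported beside it for all subjects who received at least one dose, under this rule:

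- Not in range: anyone who resumed prohibited phosphate or active vitamin D, or who has no Week 48 value.
- Observed Week 48 value used: anyone who stopped burosumab but returned without prohibited therapy.

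List each non-completer with exit reason and last phosphate Z-score, so that the reader can judge the gap without a subjective sorting of exits. Section 7.2 already has the reason for early termination recorded in the CRF. The same entry should cover subjects who stop the drug but stay in the study.

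The cost is a wording amendment, with IRB approval and the company collaborators' agreement under section 10.11.1. It needs no new visits or tests, and no dosing or withdrawal rule changes. The price in interpretation is that the all-dosed figure is lower and that exits unrelated to phosphate bias it downward: 9/15 = 60.0% (0.323–0.837) in the illustration if all five leavers lack a Week 48 value. The text should call it a conservative bound to be read with the completer figure.

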9.3.1 Evaluable for toxicity

All participants will be evaluable for toxicity from the time of their first treatment with burosomab.

9.3.2 Evaluable for objective response

Not applicable.

9.3.3 Evaluable Non-Target Disease Response

Not applicable.

9.4 Statistical Analyses

9.4.1 General Approach

We will report summary statistics such as means, standard deviation, median and interquartile range for continuous variables, and frequencies and proportions for categorical variables. The strength of statistical evidence throughout the study will be assessed using point estimates, confidence intervals, together with *p* values in drawing conclusions. For this small disease population trial, we will make all efforts to minimize the occurrence of missing data. For longitudinal continuous data, linear mixed effects models will handle the missing data under the assumption that values are missing at random. All analyses will be conducted in SAS (version 9.4, SAS Institute, Cary NC).

9.4.2 Analysis of the Primary Endpoints

The 95% Clopper-Pearson exact confidence interval will be calculated for the proportion of subjects achieving serum phosphate levels within the target range (Z-score -1 to +2) at Week 48. The primary endpoint will be evaluated in the Efficacy Analysis Dataset.

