1.2 Schema

NIH evaluation												NIH evaluation												NIH evaluation											
-2	0	2	4	6	8	10	12	14	16	18	20	22	24	26	28	30	32	34	36	38	40	42	44	46	48										
Washout period	Burosumab Treatment																																		
Subjects will be treated with burosumab for 48 weeks following a 2-week washout period. Evaluations will be performed at the NIH Clinical Center at baseline, 24, and 48 weeks. Between visits burosumab will be administered locally, and subjects will be monitored remotely with outpatient labs.																																			

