1.3 Schedule of Activities (SoA)

Abbreviated Title: Burosumab for FD

Version Date: 02/20/2024

Procedures	Week 26	Week 28	Week 30	Week 32	Week 34	Week 36	Week 38	Week 40	Week 42	Week 44	Week 46	Week 48 Visit (NIH CC) ³	Week 50
Informed consent	-	-	-	-	-	-	-	-	-	-	-	-	-
Demographics	-	-	-	-	-	-	-	-	-	-	-	-	-
Medical history	-	-	-	-	-	-	-	-	-	-	-	X	-
Physical exam (including height, arm span, and weight)	-	-	-	-	-	-	-	-	-	-	-	X	-
Vital signs	-	-	-	-	-	-	-	-	-	-	-	X	-
Injection teaching	-	-	-	-	-	-	-	-	-	-	-	-	-
Functional parameters ⁴	-	-	-	-	-	-	-	-	-	-	-	X	-
NIH lab tests ⁵	-	-	-	-	-	-	-	-	-	-	-	X	-
Outpatient lab tests ⁶	-	X	-	X	-	X	-	X	-	X	-	-	-
Pregnancy test ⁷	-	X	-	X	-	X	-	X	-	X	-	X	-
Bone biopsy ⁸	-	-	-	-	-	-	-	-	-	-	-	X	-
Imaging assessment ⁹	-	-	-	-	-	-	-	-	-	-	-	X	-
Patient reported outcomes ¹⁰	-	-	-	-	-	-	-	-	-	-	-	X	-
Burosumab administration (pediatric subjects) ¹¹	X	X	X	X	X	X	X	X	X	X	X	-	-
Burosumab administration (adult subjects) ¹¹	-	X	-	X	-	X	-	X	-	X	-	-	-
Study close-out teleconference (pediatric subjects) ¹²												X	
Adverse event review and evaluation ¹²													

¹ Informed consent will be obtained by telephone or in person prior to the baseline visit.

² Subjects receiving supplemental phosphate, active vitamin D metabolites, or current burosumab treatment will discontinue these medications for 2 weeks prior to screening.

³ Visits will be conducted in the NIH Clinical Center in the inpatient, day hospital, or clinic settings as appropriate. All visits will occur within a window of +/- 5 days from the planned timepoint.

⁴ Muscle strength, range-of-motion, 9-minute walk test.

Abbreviated Title: Burosumab for FD

Version Date: 02/20/2024

⁵ Serum sodium, potassium, chloride, bicarbonate, glucose, blood urea nitrogen, creatinine, albumin, total protein, calcium, magnesium, phosphate, parathyroid hormone, 25-hydroxyvitamin D, 1,25-dihydroxyvitamin D, aspartate aminotransferase, alanine aminotransferase, total bilirubin, alkaline phosphatase, osteocalcin, procollagen type 1 N-terminal propeptide, Beta-CrossLaps C-telopeptides, intact FGF23 (baseline visit only), C-terminal FGF23 (baseline visit only), research blood, anti-drug antibodies, neutralizing antibodies (in samples testing positive for neutralizing antibodies only), and burosumab concentration. 24-hour urinary calcium, creatinine, phosphate (toilet trained subjects), random urinary calcium, creatinine, phosphate (non-toilet trained subjects), and TmP/GFR.

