2 INTRODUCTION

2.1 Study Rationale

Fibrous dysplasia (FD) is a rare, mosaic disorder of $G\alpha_s$ activation in which normal bone and marrow are replaced with fibro-osseous tissue. Disease may involve one bone or many, and may occur in association with extraskeletal features, termed McCune-Albright syndrome (MAS) [1]. $G\alpha_s$ mutation-bearing skeletal stem cells produce excess amounts of the phosphaturic hormone fibroblast growth factor-23 (FGF23). This leads to hyperphosphaturia in most patients, and those with a high FD tissue burden may develop frank hypophosphatemia. Because FD tissue is inherently poorly mineralized and structurally unsound, it is likely at increased vulnerability to the deleterious effects of hypophosphatemia compared to typical bone. Therefore, in addition to sequelae of rickets/osteomalacia, patients with FGF23-mediated hypophosphatemia present with increased FD-related morbidity, including progressive skeletal deformities, fractures, bone pain, and functional impairment [2-4].

Like other disorders of FGF23 excess, management of hypophosphatemia in FD has traditionally focused on repletion with oral phosphate and active vitamin D analogs. However, this regimen is complicated by dose-limiting side effects, including gastrointestinal intolerance and renal toxicity. Normalization of serum phosphate is therefore not a practical goal with conventional treatment, placing patients with FD at continued risk of skeletal complications from persistent hypophosphatemia. Burosumab, a human recombinant monoclonal antibody to FGF23, represents a new, targeted treatment approach. Multiple clinical trials have demonstrated safe, efficacious use of burosumab in FGF23-mediated disorders such as X-linked hypophosphatemia (XLH) and tumor-induced osteomalacia (TIO), leading to improved serum phosphate levels and skeletal outcomes without adverse gastrointestinal or renal side effects. While the underlying pathophysiology of FGF23 excess is shared between these conditions, there is no literature regarding the use of burosumab in FD.

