Given the known limitations of conventional therapy, burosumab is an intuitive choice for management of hypophosphatemia in FD. However, additional research into the safety and efficacy of burosumab is needed before it can be used routinely in this population. The potential for FD tissue effects is an important consideration; it is unknown whether burosumab may impact skeletal stem cell proliferation or other drivers of FD lesion growth and activity. Given the increased vulnerability of FD to deleterious effects of hypophosphatemia, investigation is needed to determine if targeting a mid-normal serum phosphate level (typically unachievable with conventional therapy) is a safe and effective therapeutic goal in patients with FD. Burosumab is labeled as a subcutaneous injection administered by healthcare professionals; however, the option of self-administration would offer many benefits in the FD population, including improved accessibility, cost, and convenience. Studies are needed to determine the feasibility of this approach.

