5 STUDY POPULATION

5.1 Inclusion Criteria

In order to be eligible to participate in this study, an individual must meet all of the following criteria:

1. Confirmed diagnosis of fibrous dysplasia
2. Serum phosphate <10th percentile for age and sex, AND intact serum FGF23 ≥ 30 pg/mL[16]
3. Age ≥ 1 year
4. Provision of signed and dated informed consent/assent form

5. Stated willingness of subject or Legally Authorized Representative (LAR) to comply with all study procedures and availability for the duration of the study
6. For females of reproductive potential: agreement to use highly effective contraception for during study participation. Highly effective contraception methods include:
 - Total abstinence (when this is in line with the preferred and usual lifestyle of the participant). Periodic abstinence (e.g., calendar, ovulation, symptothermal, post-ovulation methods) and withdrawal are not acceptable methods of contraception
 - Female sterilization (have had surgical bilateral oophorectomy with or without hysterectomy) or tubal ligation at least six weeks before taking study treatment.
 - Male sterilization (at least 6 months prior to screening). For female participants on the study the vasectomized male partner should be the sole partner for that participant.
 - Combination of the following (a+b or a+c, or b+c):
 - a. Use of oral, injected or implanted hormonal methods of contraception or other forms of hormonal contraception that have comparable efficacy (failure rate <1%), for example hormone vaginal ring or transdermal hormone contraception
 - b. Placement of an intrauterine device (IUD) or intrauterine system (IUS)
 - c. Barrier methods of contraception: Condom or Occlusive cap (diaphragm or cervical/vault caps) with spermicidal foam/gel/film/cream/vaginal suppository
7. For males of reproductive potential: use of condoms or other methods described above to ensure effective contraception with partner
8. Minimum body weight of 7.5 kilograms

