5.6 Screen Failures

Screen failures are defined as subjects who consent to participate in the clinical trial but are not subsequently assigned to the study intervention or entered in the study. A minimal set of screen failure information is required to ensure transparent reporting of screen failure participants, to meet the Consolidated Standards of Reporting Trials (CONSORT) publishing requirements and to respond to queries from regulatory authorities. Minimal information includes demography, screen failure details, eligibility criteria, and any Serious Adverse Event (SAE).

Individuals who do not meet the criteria for participation in this trial (screen failure) because of an insufficiently low serum phosphate or low FGF23 level may be rescreened up to 3 times. Rescreened individuals should be assigned the same subject number as for the initial screening.

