6.1.2 Dosing and Administration

Burosomab initiation for pediatric and adult subjects will be based on currently approved regimens for XLH and TIO.

For pediatric subjects (age < 18 years) who weigh less than 10 kg, the starting dose is 1 mg/kg of body weight, rounded to the nearest 1 mg, administered every 2 weeks. For pediatric subjects who weigh 10 kg and greater, the starting dose regimen is 0.8 mg/kg of body weight, rounded to the nearest 10 mg, administered every 2 weeks. The minimum starting dose is 10 mg up to a maximum dose of 90 mg. For adults (age 18 years and older) the starting dose regimen is 0.5 mg/kg body weight, rounded to the nearest 10 mg up to a maximum dose of 90 mg, administered every 4 weeks.

After burosomab administration, doses will be titrated in an effort to achieve a target fasting peak serum phosphate level between -1 and +2 standard deviations for age and sex (**Table 5**). If the subject's peak serum phosphate level at week 2 remains below the target range, the subject's dose may be increased at week 4 by 0.2 to 0.5 mg/kg at the discretion of the Investigator. Doses will then continue to be titrated in increments of 0.2 to 0.5 mg/kg at 4-week intervals in individual subjects to achieve the target peak serum phosphate range. If the target range is not reached for patients >18 year and older, dosing may be administered at every 2-week dosing

intervals at the discretion of the PI and adjusted in increments of 0.2 to 0.5 mg/kg to a maximum dose of 90 mg every 2 weeks.

Table 5. Burosumab Target Phosphate Ranges for Pediatric and Adult Subjects

Age (years)	Normal Phosphate Range (mg/dL)	Target Peak Serum Phosphate Range (Z-score -1 to +2; mg/dL)
1 to <5	4.3 - 6.8	4.9 - 6.8
5 to <13	4.1 - 5.9	4.6 - 5.9
13 to <16 (girls)	3.2 - 5.5	3.8 - 5.5
13 to <16 (boys)	3.5 - 6.2	4.2 - 6.2
16-18	2.9 - 5	3.4 - 5
>18	2.5 - 4.5	3 - 4.5

From: summary of age and sex-partitioned reference intervals from the CALIPER study, including thousands of healthy children and adolescents from a multiethnic population and measured using the Abbot Architect analyzer [18].

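### Does the Week 48 primary analysis need a count of subjects already in the phosphate target range at Week 0?

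*Combined protocol and SAP*

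**What the plan says.** Section 9.4.2 gives the whole primary analysis: "The 95% Clopper-Pearson exact confidence interval will be calculated for the proportion of subjects achieving serum phosphate levels within the target range". That range is Z -1 to +2, the time point is Week 48, and the set is the Efficacy Analysis Dataset. Under Section 9.3, that means subjects who completed 48 weeks and returned for the visit. No Week 0 term appears.

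Eligibility (Section 5.1, criterion 2) requires "Serum phosphate <10th percentile for age and sex, AND intact serum FGF23 ≥ 30 pg/mL". The qualifying values come from the natural history protocol (Section 8.1). A person who fails "because of an insufficiently low serum phosphate or low FGF23 level may be rescreened up to 3 times" (Section 5.6). Nothing requires phosphate to be below the threshold again at Week 0.

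The baseline value is used elsewhere:
- Section 9.1 lists change and percent change in serum phosphate as a secondary endpoint. Section 9.4.3 analyses change scores with a model-based interval and p value.
- Section 9.4.5 summarises all baseline characteristics, laboratory variables included, with means, SDs, medians and interquartile ranges for continuous variables and frequencies for categorical ones.
- Section 1.2 confirms the timing: "Evaluations will be performed at the NIH Clinical Center at baseline, 24, and 48 weeks".

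**The concern.** The objective is to normalize phosphate, and with one arm the Week 0 value is the only within-subject comparator. The eligibility cut lies just under the target floor, the qualifying sample may be old or one of several attempts, and selecting on a low value invites regression to the mean. Some subjects could therefore be in range before the first dose and still count as successes at Week 48.

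The planned summaries would not reveal how many. A pooled mean or quartile in mg/dL cannot be read against age-specific limits: in Table 5, 4.0 mg/dL is in target in three bands (girls 13 to <16, 16-18, >18) and below target in the other three. With 10 subjects and the SAS default quartile, the upper quartile is the 8th ordered value, so two subjects could be in range while it sits below target. Section 9.4.8 marks individual tabulations as not applicable.

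At stake is how a middling result is read. A 7/10 result has the same Clopper-Pearson interval whether none or two of the ten began in range.

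**Working it through.** **The plan's own figure.** Clopper-Pearson limits for x of n are the 0.025 quantile of Beta(x, n-x+1) and the 0.975 quantile of Beta(x+1, n-x). For 9/10 this gives 0.555 to 0.997, width 0.44, as in Table 7. A Week 0 count would change neither this nor the sample size.

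**Gap between eligibility and target.** If phosphate is roughly normal in the reference population, the 10th percentile is Z = -1.2816, so the gap to the floor is 0.2816 SD. Taking SD as (upper - lower)/4 from the Table 5 normal ranges gives SDs of 0.45 to 0.675 mg/dL, hence gaps of 0.2816 × 0.45 = 0.13 to 0.2816 × 0.675 = 0.19 mg/dL. For adults, the mean is 3.5 and the SD 0.5, so the 10th percentile is 3.5 - 1.2816 × 0.5 = 2.86 against a floor of 3.0.

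**Chance of being in range at Week 0.** Severity and within-person SD are not in the documents and are assumed. True Z is normal with mean -1.5, -2.0 or -2.5 and between-subject SD 0.7. Independent within-person error has SD 0.3, 0.5 or 0.7. A subject enrols if the lowest of one screen (or, as an upper case, four) is below -1.2816. There is no drug effect, and the FGF23 criterion is not modelled; it would tend to lower the figures. Simulation with 2,000,000 draws per setting gives:

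| Mean Z | One screen (SD 0.3 / 0.5 / 0.7) | Four screens (SD 0.3 / 0.5 / 0.7) |
|---|---|---|
| -1.5 | 5 / 12 / 18% | 9 / 18 / 24-25% |
| -2.0 | 2 / 6 / 10% | 4 / 9 / 14% |
| -2.5 | 1 / 2 / 4-5% | 1 / 3 / 6% |

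**Washout.** If supplements stop after screening and Week 0 falls by an assumed 0.3 to 0.5 Z, the central case (mean -2.0, SD 0.5) drops from about 6% to 2.3-1.2% with one screen, and from 9% to 4.1-2.2% with four.

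**Among 10 subjects, central case (binomial).**

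| | One screen | Four screens |
|---|---|---|
| At least 1, no washout effect | 45% | 61% |
| At least 1, with washout shift | 21-11% | 34-20% |
| At least 2, no washout effect | 11% | 22% |
| At least 2, with washout shift | 2.1-0.6% | 6.1-1.9% |

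**Effect on reading the result** (N = 10, nobody leaves range). The intervals for the paired difference are exact unconditional limits from inverting the Tango score statistic.

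| Week 48 | In range at Week 0 | Paired difference (95% interval) | Clopper-Pearson |
|---|---|---|---|
| 9/10 | 0 | 0.9 (0.36-1.00) | 0.55-1.00 |
| 9/10 | 2 | 0.7 (0.22-0.93) | 0.55-1.00 |
| 7/10 | 0 | 0.7 (0.22-0.93) | 0.35-0.93 |
| 7/10 | 2 | 0.5 (0.07-0.81) | 0.35-0.93 |

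At the protocol's expected proportion of 0.9, the chance of 7/10 or fewer is 0.07. If that is independent of the Week 0 count, the chance of such a result together with two or more in range at Week 0 is 0.07 × 0.11 = 0.8% (one screen) to 0.07 × 0.22 = 1.5% (four), before any washout effect.

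**The case for a change.** The best case for a change is that the row costs nothing to produce, since phosphate is measured at both visits, and that specifying it now avoids a post hoc table. If the count were zero, saying so would strengthen the result. Moreover, the Section 9.4.5 summary covers all treated subjects while the primary set is Week 48 completers, so a baseline frequency need not match the primary denominator. And if the true proportion is nearer 0.7 than 0.9, a middling result is no longer unlikely.

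These observations are correct, and no named output gives the count. But Sections 9.4.1 and 9.4.5 already provide for categorical frequencies at baseline, so an in-target yes/no row, set against Week 48 in the completers, is a table-layout decision. Formal paired inference would not clearly help. At 7/10 with two in range at Week 0, the exact interval (0.067-0.812) excludes zero while an exact McNemar p value is 2 × 0.5^5 = 0.063; the two would point in different directions in the very case that motivates them.

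One inconsistency remains. Footnote 2 of the Schedule of Activities says subjects on these treatments "will discontinue these medications for 2 weeks prior to screening", whereas Sections 1.2, 6.5 and 8.2 place the washout between Week -2 and baseline. These passages must be reconciled. For this point it matters little: under one reading both samples are off supplements, under the other only Week 0 is, and neither would raise Week 0 relative to screening.

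**Conclusion.** No change to the plan follows. The gap is real but is one of reporting detail. The entry criterion sets the starting proportion at zero on the qualifying sample, and the protocol gives its own reason to expect few exceptions on prior therapy: "Normalization of serum phosphate is therefore not a practical goal with conventional treatment" (Section 2.1). The within-subject comparison is made through the planned analysis of change in phosphate.

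In the central case the expected number in range at Week 0 is about 0.6 to 0.9 of 10, or 0.1 to 0.4 if washout follows screening. That rests on assumed severity and variability. The least favourable cell, about 24% per subject, needs mild disease, large within-person variation and four screens for everyone. Even two such subjects would leave a 9/10 result well clear of zero. They would colour a 7/10 result, and a descriptive count, which the existing text already permits, is enough to show it. The primary proportion, its interval and Table 7 stand as written.
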